14.2.2 Plasmablast Response Against 2013 and 2017 A/H7N9

Table 80: Summary of A/Shanghai/2/2013 (A/H7N9)–Specific Antibody Secreting Cells by Immunoglobulin Type, Study Group, and Study Day, Per Protocol Population

| Time Point | Statistic | Group 1 2013 3.75+AS03/ 2017 3.75+AS03 (D1-D22) (N=X) | Group 2 2013 3.75+AS03/ 2017 3.75+AS03 (D1-D121) (N=X) | Group 3 2013 3.75+AS03/ 2017 15 (D1-D121) (N=X) | Group 4 2017 3.75+AS03/ 2017 3.75+AS03 (D1-D22) (N=X) | Group 5 2017 3.75+AS03/ 2017 3.75+AS03 (D1-D121) (N=X) | Group 6 2017 3.75+AS03/ 2017 15 (D1-D121) (N=X) |
|-------------------------------------|--------------|---|--|---|---|--|---|
| IgA Antibody Secreting Cells | | | | | | | |
| Day 8 Post Vac 1 | n | x | x | x | x | x | x |
| | Mean (SD) | xx.x (xx.x,xx.x) | xx.x (xx.x,xx.x) | xx.x (xx.x,xx.x) | xx.x (xx.x,xx.x) | xx.x (xx.x,xx.x) | xx.x (xx.x,xx.x) |
| | 95% CI | xx.x, xx.x | xx.x, xx.x | xx.x, xx.x | xx.x, xx.x | xx.x, xx.x | xx.x, xx.x |
| | Median [IQR] | xx [xx, xx] | xx [xx, xx] | xx [xx, xx] | xx [xx, xx] | xx [xx, xx] | xx [xx, xx] |
| | Min, Max | xx, xx | xx, xx | xx, xx | xx, xx | xx, xx | xx, xx |
| Day 8 Post Vac 2 ^a | n | x | x | x | x | x | x |
| | Mean (SD) | xx.x (xx.x,xx.x) | xx.x (xx.x,xx.x) | xx.x (xx.x,xx.x) | xx.x (xx.x,xx.x) | xx.x (xx.x,xx.x) | xx.x (xx.x,xx.x) |
| | 95% CI | xx.x, xx.x | xx.x, xx.x | xx.x, xx.x | xx.x, xx.x | xx.x, xx.x | xx.x, xx.x |
| | Median [IQR] | xx [xx, xx] | xx [xx, xx] | xx [xx, xx] | xx [xx, xx] | xx [xx, xx] | xx [xx, xx] |
| | Min, Max | xx, xx | xx, xx | xx, xx | xx, xx | xx, xx | xx, xx |
| IgG Antibody Secreting Cells | | | | | | | |
| Day 8 Post Vac 1 | n | x | x | x | x | x | x |
| | Mean (SD) | xx.x (xx.x,xx.x) | xx.x (xx.x,xx.x) | xx.x (xx.x,xx.x) | xx.x (xx.x,xx.x) | xx.x (xx.x,xx.x) | xx.x (xx.x,xx.x) |
| | 95% CI | xx.x, xx.x | xx.x, xx.x | xx.x, xx.x | xx.x, xx.x | xx.x, xx.x | xx.x, xx.x |
| | Median [IQR] | xx [xx, xx] | xx [xx, xx] | xx [xx, xx] | xx [xx, xx] | xx [xx, xx] | xx [xx, xx] |
| | Min, Max | xx, xx | xx, xx | xx, xx | xx, xx | xx, xx | xx, xx |
| | n | x | x | x | x | x | x |

| Time Point | Statistic | Group 1 2013 3.75+AS03/ 2017 3.75+AS03 (D1-D22) (N=X) | Group 2 2013 3.75+AS03/ 2017 3.75+AS03 (D1-D121) (N=X) | Group 3 2013 3.75+AS03/ 2017 15 (D1-D121) (N=X) | Group 4 2017 3.75+AS03/ 2017 3.75+AS03 (D1-D22) (N=X) | Group 5 2017 3.75+AS03/ 2017 3.75+AS03 (D1-D121) (N=X) | Group 6 2017 3.75+AS03/ 2017 15 (D1-D121) (N=X) |
|--|-----------------|---|--|---|---|--|---|
| Day 8 Post Vac 2 ^a | Mean (SD) | xx.x (xx.x,xx.x) | xx.x (xx.x,xx.x) | xx.x (xx.x,xx.x) | xx.x (xx.x,xx.x) | xx.x (xx.x,xx.x) | xx.x (xx.x,xx.x) |
| | 95% CI | xx.x, xx.x | xx.x, xx.x | xx.x, xx.x | xx.x, xx.x | xx.x, xx.x | xx.x, xx.x |
| | Median [IQR] | xx [xx, xx] | xx [xx, xx] | xx [xx, xx] | xx [xx, xx] | xx [xx, xx] | xx [xx, xx] |
| | Min, Max | xx, xx | xx, xx | xx, xx | xx, xx | xx, xx | xx, xx |
| IgM Antibody Secreting Cells | | | | | | | |
| Day 8 Post Vac 1 | n | x | x | x | x | x | x |
| | Mean (SD) | xx.x (xx.x,xx.x) | xx.x (xx.x,xx.x) | xx.x (xx.x,xx.x) | xx.x (xx.x,xx.x) | xx.x (xx.x,xx.x) | xx.x (xx.x,xx.x) |
| | 95% CI | xx.x, xx.x | xx.x, xx.x | xx.x, xx.x | xx.x, xx.x | xx.x, xx.x | xx.x, xx.x |
| | Median [IQR] | xx [xx, xx] | xx [xx, xx] | xx [xx, xx] | xx [xx, xx] | xx [xx, xx] | xx [xx, xx] |
| | Min, Max | xx, xx | xx, xx | xx, xx | xx, xx | xx, xx | xx, xx |
| Day 8 Post Vac 2 ^a | n | x | x | x | x | x | x |
| | Mean (SD) | xx.x (xx.x,xx.x) | xx.x (xx.x,xx.x) | xx.x (xx.x,xx.x) | xx.x (xx.x,xx.x) | xx.x (xx.x,xx.x) | xx.x (xx.x,xx.x) |
| | 95% CI | xx.x, xx.x | xx.x, xx.x | xx.x, xx.x | xx.x, xx.x | xx.x, xx.x | xx.x, xx.x |
| | Median [IQR] | xx [xx, xx] | xx [xx, xx] | xx [xx, xx] | xx [xx, xx] | xx [xx, xx] | xx [xx, xx] |
| | Min, Max | xx, xx | xx, xx | xx, xx | xx, xx | xx, xx | xx, xx |
| N = Number of subjects in the Modified Intent-to-Treat Population; n = number of subjects with results reported. | | | | | | | |
| ^a Day 8 post vaccination 2 varies by group (Day 29 for Groups 1 and 4; Day 128 for Groups 2, 3,5, and 6). | | | | | | | |

Table with similar format:

Table 81: Summary of A/Hong Kong/125/2017 (A/H7N9)–Specific Antibody Secreting Cells by Immunoglobulin Type, Study Group, and Study Day, Per Protocol Population

14.3 Safety Data

14.3.1 Displays of Adverse Events

Table 82: Overall Summary of Adverse Events, Safety Population*

| AE Category | AE Subcategory | Group 1 2013 3.75+AS03/ 2017 3.75+AS03 (D1-D22) (N=X) | | Group 2 2013 3.75+AS03/ 2017 3.75+AS03 (D1-D121) (N=X) | | Group 3 2013 3.75+AS03/ 2017 15 (D1-D121) (N=X) | | Group 4 2017 3.75+AS03/ 2017 3.75+AS03 (D1-D22) (N=X) | | Group 5 2017 3.75+AS03/ 2017 3.75+AS03 (D1-D121) (N=X) | | Group 6 2017 3.75+AS03/ 2017 15 (D1-D121) (N=X) | | All Subjects (N=X) | |
|---|--------------------|---|---|--|---|--|---|---|---|--|---|--|---|--------------------------|---|
| | | n | % | n | % | n | % | n | % | n | % | n | % | n | % |
| Subjects^a with | | | | | | | | | | | | | | | |
| At least one local solicited adverse event | - | x | x | x | x | x | x | x | x | x | x | x | x | x | x |
| At least one systemic solicited adverse event | - | x | x | x | x | x | x | x | x | x | x | x | x | x | x |
| At least one laboratory adverse event | Any Grade | x | x | x | x | x | x | x | x | x | x | x | x | x | x |
| | Mild (Grade 1) | x | x | x | x | x | x | x | x | x | x | x | x | x | x |
| | Moderate (Grade 2) | x | x | x | x | x | x | x | x | x | x | x | x | x | x |
| | Severe (Grade 3) | x | x | x | x | x | x | x | x | x | x | x | x | x | x |
| At least one unsolicited adverse event | - | x | x | x | x | x | x | x | x | x | x | x | x | x | x |
| At least one related unsolicited adverse event | Any Grade | x | x | x | x | x | x | x | x | x | x | x | x | x | x |
| | Mild (Grade 1) | x | x | x | x | x | x | x | x | x | x | x | x | x | x |
| | Moderate (Grade 2) | x | x | x | x | x | x | x | x | x | x | x | x | x | x |
| | Severe (Grade 3) | x | x | x | x | x | x | x | x | x | x | x | x | x | x |
| At least one severe (Grade 3) unsolicited adverse event | Any Relationship | x | x | x | x | x | x | x | x | x | x | x | x | x | x |
| | Related | x | x | x | x | x | x | x | x | x | x | x | x | x | x |
| | Unrelated | x | x | x | x | x | x | x | x | x | x | x | x | x | x |

| AE Category | AE Subcategory | Group 1 2013 3.75+AS03/ 2017 3.75+AS03 (D1-D22) (N=X) | | Group 2 2013 3.75+AS03/ 2017 3.75+AS03 (D1-D121) (N=X) | | Group 3 2013 3.75+AS03/ 2017 15 (D1-D121) (N=X) | | Group 4 2017 3.75+AS03/ 2017 3.75+AS03 (D1-D22) (N=X) | | Group 5 2017 3.75+AS03/ 2017 3.75+AS03 (D1-D121) (N=X) | | Group 6 2017 3.75+AS03/ 2017 15 (D1-D121) (N=X) | | All Subjects (N=X) | |
|--|----------------|---|---|--|---|--|---|---|---|--|---|--|---|--------------------------|---|
| | | n | % | n | % | n | % | n | % | n | % | n | % | n | % |
| Subjects ^a with | | | | | | | | | | | | | | | |
| At least one serious adverse event ^b | - | x | x | x | x | x | x | x | x | x | x | x | x | x | x |
| At least one related, serious adverse event | - | x | x | x | x | x | x | x | x | x | x | x | x | x | x |
| At least one adverse event leading to early termination ^c | - | x | x | x | x | x | x | x | x | x | x | x | x | x | x |
| At least one medically attended adverse event | - | x | x | x | x | x | x | x | x | x | x | x | x | x | x |
| At least one new onset chronic medical condition | - | x | x | x | x | x | x | x | x | x | x | x | x | | |
| At least one potentially immune mediated medical condition | - | x | x | x | x | x | x | x | x | x | x | x | x | | |

N = Number of subjects who received at least one study vaccination; n= Number of subjects in the indicated category

^a Subjects are counted once for each category regardless of the number of events.

^b A listing of Serious Adverse Events is included in [Error! Reference source not found.](#)

^c As reported on the Adverse Event eCRF.

Table 83: Number of Adverse Events Occurring in 5% of Subjects in Any Study Group by MedDRA® System Organ Class and Preferred Term, and Study Group, Safety Population

[Implementation Note: this table combines all adverse events – solicited events, unsolicited events, and clinical laboratory events. Sort data by SOC then PT. If >= X SAEs are reported, repeat this table for all reported SAEs]

| MedDRA System Organ Class | Preferred Term | Group 1 2013 3.75+AS03/ 2017 3.75+AS03 (D1-D22) (N=X) | | | Group 2 2013 3.75+AS03/ 2017 3.75+AS03 (D1-D121) (N=X) | | | Group 3 2013 3.75+AS03/ 2017 15 (D1-D121) (N=X) | | | Group 4 2017 3.75+AS03/ 2017 3.75+AS03 (D1-D22) (N=X) | | | Group 5 2017 3.75+AS03/ 2017 3.75+AS03 (D1-D121) (N=X) | | | Group 6 2017 3.75+AS03/ 2017 15 (D1-D121) (N=X) | | | All Subjects (N=X) | | |
|------------------------------------|----------------|---|---|--------|--|---|--------|--|---|--------|---|---|--------|--|---|--------|--|---|--------|-----------------------|---|--------|
| | | n | % | Events | n | % | Events | n | % | Events | n | % | Events | n | % | Events | n | % | Events | n | % | Events |
| Serious Adverse Events | | | | | | | | | | | | | | | | | | | | | | |
| All | All | x | x | x | x | x | x | x | x | x | x | x | x | x | x | x | x | x | x | x | x | |
| SOC1 | PT1 | x | x | x | x | x | x | x | x | x | x | x | x | x | x | x | x | x | x | x | x | |
| Etc. | Etc. | | | | | | | | | | | | | | | | | | | | | |
| Other (Non-serious) Adverse Events | | | | | | | | | | | | | | | | | | | | | | |
| All | All | x | x | x | x | x | x | x | x | x | x | x | x | x | x | | | | | x | x | |
| SOC1 | PT1 | x | x | x | x | x | x | x | x | x | x | x | x | x | x | | | | | x | x | |
| Etc. | Etc. | | | | | | | | | | | | | | | | | | | | | |

N = number of subjects in the Safety Population (number of subjects at risk); n= number of subjects reporting event. Events = total frequency of events reported.
MedDRA Version X.X.

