8.3 Final Visit

8.3.1 Safety Follow-up, Phone Call, All Treatment Arms

**Visit 16, Day 387 (Window: Day 366±14 days post second study vaccination),
Treatment Arms 1 and 4**

**Visit 18, Day 486 (Window: Day 366±14 days post second study vaccination),
Treatment Arms 2, 3, 5, and 6**

Subjects will be contacted by phone to query for safety events. AEs limited to SAEs and MAAEs, including NOCMCs and PIMMCs, that have occurred since the previous clinic visit or phone call will be solicited. Based on the information collected, subjects may be asked to return to the clinic for evaluation.

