3.2. Endpoints

3.2.1. Primary

Safety:

- Occurrence of all serious adverse events (SAEs) from the time of the first study vaccination through approximately 12 months after the last study vaccination.
- Occurrence of solicited injection site and systemic reactogenicity events from the time of each study vaccination through 7 days after each study vaccination.
- Occurrence of clinical safety laboratory AEs from the time of each study vaccination through approximately 7 days after each study vaccination.

Immunogenicity:

- For HAI and Neut antibodies, percentage of subjects achieving seroconversion against the influenza A/H7N9 study vaccine viruses (defined as either a pre-vaccination titer <1:10 and a post-vaccination titer ≥1:40 or a pre-vaccination titer ≥1:10 and a minimum four-fold rise in post-vaccination antibody titer) approximately 21 days after the second study vaccination.
- For HAI and Neut antibodies, percentage of subjects achieving titer ≥1:40 against the influenza A/H7N9 study vaccine viruses approximately 21 days after the second study vaccination.
- Geometric mean titers (GMTs) of serum HAI and Neut antibodies against the influenza A/H7N9 study vaccine viruses approximately 21 days after the second study vaccination.

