9.3.2. Unsolicited Adverse Events

When calculating the incidence of unsolicited AEs (i.e., on a per subject basis), each subject will only be counted once at the highest severity and/or relationship, and any repetitions of AEs within a subject will be ignored; the denominator will be the total number of subjects in the safety population. All AEs reported will be included in the summaries and analyses.

The number and percentage of subjects reporting at least one unsolicited AE will be summarized by MedDRA system organ class and preferred term. A 95% CI will be presented for the percentage of subjects reporting any unsolicited AE (serious or non-serious) for each MedDRA system organ class and preferred term over all study vaccinations ([Table 97](#)).

The following summaries for unsolicited AEs will be presented by MedDRA system organ class, preferred term, and study group:

- Incidence of AEs by severity and relationship to study product ([Table 98](#), [Table 99](#));
- Incidence of non-serious, related AEs by severity ([Table 100](#), [Table 101](#));
- Incidence of AEs over time (Days 1-8, Days 9-22 post each study vaccination) ([Table 102](#));
- Incidence of non-serious, related AEs over time (Days 1-8, Days 9-22 post each study vaccination) ([Table 103](#)) – note this table presents results for secondary safety endpoint, “Occurrence of study vaccine-related unsolicited non-serious AEs from the time of each study vaccination through approximately 21 days after each study vaccination”;
- Total frequency of AEs over time (Days 1-8, Day 9 through approximately Day22 post each study vaccination) ([Table 104](#), [Table 105](#));
- Subject listing of non-serious AEs of moderate or greater severity ([Table 110](#));
- Bar chart displaying total frequency of AEs by severity and MedDRA system organ class and study group ([Figure 28](#), [Figure 29](#));
- Bar chart displaying incidence of AEs by severity and MedDRA system organ class, and study group ([Figure 30](#), [Figure 31](#));
- Bar chart displaying total frequency and incidence of AEs by relationship to study product, MedDRA system organ class, and study group ([Figure 32](#), [Figure 33](#), [Figure 34](#), [Figure 35](#)).

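### SAP Table 82 shows crude SAE, MAAE, NOCMC and PIMMC percentages side by side by arm, although the 4-month arms are followed about 26% longer (about 49% longer at the topline cut).

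*SAP*

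**What the plan says.** SAP 3.2.1 defines the primary SAE endpoint as "Occurrence of all serious adverse events (SAEs) from the time of the first study vaccination through approximately 12 months after the last study vaccination". SAP 3.2.2 gives MAAEs, including NOCMCs and PIMMCs, the same period as a secondary endpoint. Because the period is anchored to the last dose, Protocol 8.3.1 places the final safety call at "Visit 16, Day 387" for Arms 1 and 4 and at "Visit 18, Day 486" for Arms 2, 3, 5 and 6.

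The Table 82 shell, "Overall Summary of Adverse Events, Safety Population", has one column per group, with rows such as "At least one serious adverse event" and matching rows for MAAE, NOCMC and PIMMC. Each subject counts once per row, and N is the number of subjects with at least one study vaccination. For unsolicited AEs in general, SAP 9.3.2 says "the denominator will be the total number of subjects in the safety population" and brings every reported AE into the summaries. Table 82 carries the topline asterisk. SAP 6.2.1 runs the primary clinical database to about 180 days after the last vaccination and treats the topline tables as the final analysis of those data.

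Neither document plans person-time, exposure-adjusted rates, a matched window or a follow-up footnote for these rows.

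**The concern.** The interval between doses (21 days or 4 months) is a randomised design factor, and SAE and MAAE occurrence are primary and secondary safety outcomes. A percentage of subjects with at least one event grows with observation time. When the arms of one interval are watched longer by design, a reader who looks across Table 82 sees schedule and observation time mixed together. The distortion has a known direction: it makes the 4-month arms look worse.

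The extra time is actively observed. Protocol 8.2.6 gives the 4-month arms an additional Day 61 call, before dose 2, that asks about SAEs and MAAEs. As a topline table, Table 82 may also reach the sponsor for planning later trials, and the lead investigator for publication, before the full follow-up is in.

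**Working it through.** **Inputs.** Dose 2 is on Day 22 or Day 121, and the final call is on Day 366 after dose 2 (Protocol 8.3.1). The 180-day visit is on Day 181 after dose 2 (Protocol 8.2.16). Dose 2 windows are 21–28 and 113–134 days after dose 1 (SAP 4.4.5). The documents give no event rates for this trial, so the rates below are assumptions, taken as constant over time and equal in all arms.

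**The plan's own days.** 22 + 366 − 1 = 387 and 121 + 366 − 1 = 486; 22 + 181 − 1 = 202 and 121 + 181 − 1 = 301. All four match the protocol.

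**Follow-up ratio.**
- Final report: (486 − 1)/(387 − 1) = 485/386 = 1.26.
- Topline, if every subject is cut at the 180-day visit: 300/201 = 1.49.
- Extremes of the visit windows: (113 + 351)/(28 + 379) = 464/407 = 1.14, and (134 + 379)/(21 + 351) = 513/372 = 1.38.
- Missed second doses: Protocol 11.4.2 expects about 10% (4-month) and 5% (21-day) per-protocol exclusions. If all of these missed dose 2 and were followed 12 months from dose 1, the ratio is (0.9 × 485 + 0.1 × 365)/(0.95 × 386 + 0.05 × 365) = 473.0/384.95 = 1.23.

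**Expected percentage with at least one event**, 1 − exp(−rate × days/365.25), 21-day v 4-month arms (gaps taken before rounding):

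| Assumed rate per person-year | Final, 386 v 485 days | Gap (points) | Topline, 201 v 300 days | Gap (points) |
|---|---|---|---|---|
| 0.02 | 2.1 v 2.6 | 0.5 | 1.1 v 1.6 | 0.5 |
| 0.1 | 10.0 v 12.4 | 2.4 | 5.4 v 7.9 | 2.5 |
| 0.3 | 27.2 v 32.9 | 5.7 | 15.2 v 21.8 | 6.6 |
| 0.5 | 41.0 v 48.5 | 7.5 | 24.1 v 33.7 | 9.6 |
| 1.0 | 65.2 v 73.5 | 8.3 | 42.3 v 56.0 | 13.7 |

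At 0.02 per person-year the final gap is 0.63 against 0.79 subjects in an arm of 30.

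**Chance that the pooled 4-month arms (120 subjects) show the higher final percentage than the pooled 21-day arms (60)**, by exact binomial enumeration with ties counted separately: 0.50 at 0.01, 0.66 at 0.1 and 0.82 at 0.5 per person-year. With equal follow-up of 386 days the same chances are 0.43, 0.47 and 0.48.

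**All-period unsolicited AE rows (Tables 97, 98 and 100).** Non-serious unsolicited AEs are collected for about 21 + 21 = 42 days in every arm; only SAEs and MAAEs outside that window see unequal time. Let q be the share of subjects with an event in the 42 days and r the MAAE rate outside it. The percentage is then 1 − (1 − q) × exp(−r × (days − 42)/365.25). With q assumed at 30–50% and r at 0.1–0.5, the gap is 1.2 points (54.5 v 55.7) to 5.5 points (56.3 v 61.8). The ratio is 1.02 to 1.10.

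**The case against.** The strongest case on the other side is that nothing in the plan compares these percentages. Protocol 11.6.2 expects few SAEs, MAAEs, NOCMCs and PIMMCs and relies on detailed listings. SAP 9.4 plans the same listings, and the shells show days after the associated vaccination. SAP 6.8 disclaims any specific null hypothesis, and the safety regression with an interval term (SAP 9.3.1) covers solicited events only, whose windows are equal. The Table 82 column heads also show the dosing days. This stands: the table is descriptive, and a reader who inferred a planned between-arm test of these categories would be wrong. It does not remove the point, because descriptive percentages printed side by side are read across, and dosing days alone do not tell the reader how long each group was followed.

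A second objection is size. A gap of 6 to 8 points is small beside the 31–69% interval for a single arm of 30 (Protocol Table 13), and at low rates it cannot be seen. This stands for SAEs and PIMMCs. For MAAEs, however, the shift is systematic, and wide intervals do not correct it.

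A third is that matched windows already exist for unsolicited AEs: Tables 99 and 101–103 and Figures 29, 31, 33 and 35 are limited to 21 days. That is correct and narrows the point. Those displays give no equal-time summary of the MAAE, NOCMC or PIMMC categories.

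Finally, the obvious remedy of cutting every arm at Day 387 creates the opposite imbalance after the boost: 387 − 121 = 266 days in the 4-month arms against 387 − 22 = 365 in the others. Person-year rates also assume a roughly constant hazard; if events cluster near the doses, the long inter-dose gap dilutes them. Both cautions stand and shape the fix.

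**Conclusion.** The point holds as a reporting weakness in Table 82. Planned follow-up differs by a factor of about 1.26 in the final report and about 1.49 at the topline cut, and no planned display allows for it. Under equal, constant rates the 4-month arms tend to show the higher percentage. This is material mainly for MAAEs: about 6 to 8 points in the final report at assumed rates of 0.3 to 1.0 per person-year. At 0.02 per person-year or less it is about 0.5 point or less. The ratios rest on the planned visit days; the point gaps rest on assumed rates. The topline figures also assume a per-subject cut at the 180-day visit, as the definition of the primary clinical database implies.

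Two stronger readings are tempting and not supported. One is that the 26% applies to all unsolicited AEs. The non-serious ones have the same collection time in every arm, so only late SAEs and MAAEs distort the all-period tables, and by a ratio of about 1.02 to 1.10 under the assumptions shown. The other is that an excess will appear in the 4-month arms for every category. It is an expected tendency, and at SAE- or PIMMC-like rates chance dominates it with 30 per arm.

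**What to change.** For SAE, MAAE, NOCMC and PIMMC in Table 82:

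- Add person-time at risk and events per person-year by arm, with exact Poisson 95% confidence intervals.
- Add percentages in windows matched by dose, for example dose 1 through Day 22, and dose 2 through about 180 days (topline) or about 12 months (final report). Use subjects who received the relevant dose as the denominator.
- Footnote planned follow-up by group, and state that the all-period percentages are not comparable between the two intervals.

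Do not rely on a Day 387 cut alone. The dose-matched windows leave out the time between Day 22 and dose 2 in the 4-month arms; the person-year rows keep those events. Read together, the two displays help to check the constant-hazard assumption.

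The cost is a few extra rows in one table. Event timing is already collected for the listings, so no new data are needed.

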14.3.1.1 Solicited Adverse Events

Table 84: Number and Percentage of Subjects Experiencing Solicited Events with 95% Confidence Intervals by Symptom and Study Group (Safety Population) – Post Any Study Vaccination

| Symptom | Group 1 2013 3.75+AS03/ 2017 3.75+AS03 (D1-D22) (N=X) | | Group 2 2013 3.75+AS03/ 2017 3.75+AS03 (D1-D121) (N=X) | | Group 3 2013 3.75+AS03/ 2017 15 (D1-D121) (N=X) | | Group 4 2017 3.75+AS03/ 2017 3.75+AS03 (D1-D22) (N=X) | | Group 5 2017 3.75+AS03/ 2017 3.75+AS03 (D1-D121) (N=X) | | Group 6 2017 3.75+AS03/ 2017 15 (D1-D121) (N=X) | | All Subjects (N=X) | |
|----------------------|--|------------------|---|------------------|--|------------------|--|------------------|---|------------------|--|------------------|-----------------------|------------------|
| | n | % (95% CI) | n | % (95% CI) | n | % (95% CI) | n | % (95% CI) | n | % (95% CI) | n | % (95% CI) | n | % (95% CI) |
| Any Symptom | x | xx (xx-xx) | x | xx (xx-xx) | x | xx (xx-xx) | x | xx (xx-xx) | x | xx (xx-xx) | x | xx (xx-xx) | x | xx (xx-xx) |
| Any Systemic Symptom | x | xx (xx-xx) | x | xx (xx-xx) | x | xx (xx-xx) | x | xx (xx-xx) | x | xx (xx-xx) | x | xx (xx-xx) | x | xx (xx-xx) |
| Fever | x | xx (xx-xx) | x | xx (xx-xx) | x | xx (xx-xx) | x | xx (xx-xx) | x | xx (xx-xx) | x | xx (xx-xx) | x | xx (xx-xx) |
| Feverishness | x | xx (xx-xx) | x | xx (xx-xx) | x | xx (xx-xx) | x | xx (xx-xx) | x | xx (xx-xx) | x | xx (xx-xx) | x | xx (xx-xx) |
| Fatigue | x | xx (xx-xx) | x | xx (xx-xx) | x | xx (xx-xx) | x | xx (xx-xx) | x | xx (xx-xx) | x | xx (xx-xx) | x | xx (xx-xx) |
| Malaise | x | xx (xx-xx) | x | xx (xx-xx) | x | xx (xx-xx) | x | xx (xx-xx) | x | xx (xx-xx) | x | xx (xx-xx) | x | xx (xx-xx) |
| Myalgia | x | xx (xx-xx) | x | xx (xx-xx) | x | xx (xx-xx) | x | xx (xx-xx) | x | xx (xx-xx) | x | xx (xx-xx) | x | xx (xx-xx) |
| Arthralgia | x | xx (xx-xx) | x | xx (xx-xx) | x | xx (xx-xx) | x | xx (xx-xx) | x | xx (xx-xx) | x | xx (xx-xx) | x | xx (xx-xx) |
| Headache | x | xx (xx-xx) | x | xx (xx-xx) | x | xx (xx-xx) | x | xx (xx-xx) | x | xx (xx-xx) | x | xx (xx-xx) | x | xx (xx-xx) |

| Symptom | Group 1 2013 3.75+AS03/ 2017 3.75+AS03 (D1-D22) (N=X) | | Group 2 2013 3.75+AS03/ 2017 3.75+AS03 (D1-D121) (N=X) | | Group 3 2013 3.75+AS03/ 2017 15 (D1-D121) (N=X) | | Group 4 2017 3.75+AS03/ 2017 3.75+AS03 (D1-D22) (N=X) | | Group 5 2017 3.75+AS03/ 2017 3.75+AS03 (D1-D121) (N=X) | | Group 6 2017 3.75+AS03/ 2017 15 (D1-D121) (N=X) | | All Subjects (N=X) | |
|-----------------------------------|--|------------------|---|------------------|--|------------------|--|------------------|---|------------------|--|------------------|-----------------------|------------------|
| | n | % (95% CI) | n | % (95% CI) | n | % (95% CI) | n | % (95% CI) | n | % (95% CI) | n | % (95% CI) | n | % (95% CI) |
| Nausea | x | xx (xx-xx) | x | xx (xx-xx) | x | xx (xx-xx) | x | xx (xx-xx) | x | xx (xx-xx) | x | xx (xx-xx) | x | xx (xx-xx) |
| Any Local Symptom | x | xx (xx-xx) | x | xx (xx-xx) | x | xx (xx-xx) | x | xx (xx-xx) | x | xx (xx-xx) | x | xx (xx-xx) | x | xx (xx-xx) |
| Pain | x | xx (xx-xx) | x | xx (xx-xx) | x | xx (xx-xx) | x | xx (xx-xx) | x | xx (xx-xx) | x | xx (xx-xx) | x | xx (xx-xx) |
| Tenderness | x | xx (xx-xx) | x | xx (xx-xx) | x | xx (xx-xx) | x | xx (xx-xx) | x | xx (xx-xx) | x | xx (xx-xx) | x | xx (xx-xx) |
| Pruritus | x | xx (xx-xx) | x | xx (xx-xx) | x | xx (xx-xx) | x | xx (xx-xx) | x | xx (xx-xx) | x | xx (xx-xx) | x | xx (xx-xx) |
| Ecchymosis | x | xx (xx-xx) | x | xx (xx-xx) | x | xx (xx-xx) | x | xx (xx-xx) | x | xx (xx-xx) | x | xx (xx-xx) | x | xx (xx-xx) |
| Ecchymosis (measurement) | x | xx (xx-xx) | x | xx (xx-xx) | x | xx (xx-xx) | x | xx (xx-xx) | x | xx (xx-xx) | x | xx (xx-xx) | x | xx (xx-xx) |
| Erythema | x | xx (xx-xx) | x | xx (xx-xx) | x | xx (xx-xx) | x | xx (xx-xx) | x | xx (xx-xx) | x | xx (xx-xx) | x | xx (xx-xx) |
| Erythema (measurement) | x | xx (xx-xx) | x | xx (xx-xx) | x | xx (xx-xx) | x | xx (xx-xx) | x | xx (xx-xx) | x | xx (xx-xx) | x | xx (xx-xx) |
| Induration/Swelling | x | xx (xx-xx) | x | xx (xx-xx) | x | xx (xx-xx) | x | xx (xx-xx) | x | xx (xx-xx) | x | xx (xx-xx) | x | xx (xx-xx) |
| Induration/Swelling (measurement) | x | xx (xx-xx) | x | xx (xx-xx) | x | xx (xx-xx) | x | xx (xx-xx) | x | xx (xx-xx) | x | xx (xx-xx) | x | xx (xx-xx) |

| Symptom | Group 1 2013 3.75+AS03/ 2017 3.75+AS03 (D1-D22) (N=X) | | Group 2 2013 3.75+AS03/ 2017 3.75+AS03 (D1-D121) (N=X) | | Group 3 2013 3.75+AS03/ 2017 15 (D1-D121) (N=X) | | Group 4 2017 3.75+AS03/ 2017 3.75+AS03 (D1-D22) (N=X) | | Group 5 2017 3.75+AS03/ 2017 3.75+AS03 (D1-D121) (N=X) | | Group 6 2017 3.75+AS03/ 2017 15 (D1-D121) (N=X) | | All Subjects (N=X) | |
|--|--|------------------|---|------------------|--|---------------|--|------------------|---|------------------|--|------------------|-----------------------|------------------|
| | n | % (95% CI) | n | % (95% CI) | n | % (95% CI) | n | % (95% CI) | n | % (95% CI) | n | % (95% CI) | n | % (95% CI) |
| N = Number of subjects in the Safety Population who received any study vaccination; n = Number of subjects reporting event 95% CI estimated using the Clopper-Pearson exact method | | | | | | | | | | | | | | |

Tables with similar format:

Table 85: Number and Percentage of Subjects Experiencing Solicited Events with 95% Confidence Intervals by Symptom and Study Group (Safety Population) – Post Study Vaccination 1

[Footnote update] N = Number of subjects in the Safety Population who received the first study vaccination.

Table 86: Number and Percentage of Subjects Experiencing Solicited Events with 95% Confidence Intervals by Symptom and Study Group (Safety Population) – Post Study Vaccination 2

[Footnote update] N = Number of subjects in the Safety Population who received the second study vaccination.

Table 87: Logistic Regression Model to Evaluate the Relationship of Study Vaccination with Reporting Any Local Event Post Second Study Vaccination, Safety Population

[Implementation Note: If statistically significant effects (defined as p-value <0.05) are observed in the model for local events then this table should be repeated for additional models which will be fit for each individual local event. Any solicited local event grade 1 or higher reported within 7 days of study vaccination will count as a reported event.]

| Model Parameter | Parameter Category | Parameter Estimate | SE | p-value | Odds Ratio | 95%CI |
|-----------------|------------------------|--------------------|-------|---------|------------|-----------|
| Intercept | N/A | xxx.x | xxx.x | x.xxx | - | - |
| Prime-boost | Homologous (reference) | - | - | - | - | - |
| | Heterologous | xxx.x | xxx.x | x.xxx | xx.x | xx.x-xx.x |
| Boost Dose | 15 mcg (reference) | - | - | - | - | - |
| | 3.75 mcg + AS03 | xxx.x | xxx.x | x.xxx | xx.x | xx.x-xx.x |
| Interval | 21 days (reference) | - | - | - | - | - |
| | 120 days | xxx.x | xxx.x | x.xxx | xx.x | xx.x-xx.x |

N = XX (number of subjects in the Safety Population)

Table with similar format:

Table 88: Logistic Regression Model to Evaluate the Relationship of Study Vaccination with Reporting Any Systemic Event Post Second Study Vaccination, Safety Population

[Implementation Note: If statistically significant effects defined p-value <0.05 are observed in the model for systemic events then this table should be repeated for additional models which will be fit for each individual systemic event. Any solicited systemic event grade 1 or higher reported within 7 days of study vaccination will count as a reported event.]

Table 89: Number and Percentage of Subjects Experiencing Solicited Events by Symptom, Maximum Severity and Study Group (Safety Population) – Post Any Study Vaccination

| Symptom | Severity | Group 1 2013 3.75+AS03/ 2017 3.75+AS03 (D1-D22) (N=X) | | Group 2 2013 3.75+AS03/ 2017 3.75+AS03 (D1-D121) (N=X) | | Group 3 2013 3.75+AS03/ 2017 15 (D1-D121) (N=X) | | Group 4 2017 3.75+AS03/ 2017 3.75+AS03 (D1-D22) (N=X) | | Group 5 2017 3.75+AS03/ 2017 3.75+AS03 (D1-D121) (N=X) | | Group 6 2017 3.75+AS03/ 2017 15 (D1-D121) (N=X) | | All Subjects (N=X) | |
|----------------------|----------|--|---------------|---|---------------|--|---------------|--|---------------|---|---------------|--|---------------|-----------------------|---------------|
| | | n | % (95% CI) | n | % (95% CI) | n | % (95% CI) | n | % (95% CI) | n | % (95% CI) | n | % (95% CI) | n | % (95% CI) |
| Any Symptom | None | x | xx (xx-xx) | x | xx (xx-xx) | x | xx (xx-xx) | x | xx (xx-xx) | x | xx (xx-xx) | x | xx (xx-xx) | x | xx (xx-xx) |
| | Mild | x | xx (xx-xx) | x | xx (xx-xx) | x | xx (xx-xx) | x | xx (xx-xx) | x | xx (xx-xx) | x | xx (xx-xx) | x | xx (xx-xx) |
| | Moderate | x | xx (xx-xx) | x | xx (xx-xx) | x | xx (xx-xx) | x | xx (xx-xx) | x | xx (xx-xx) | x | xx (xx-xx) | x | xx (xx-xx) |
| | Severe | x | xx (xx-xx) | x | xx (xx-xx) | x | xx (xx-xx) | x | xx (xx-xx) | x | xx (xx-xx) | x | xx (xx-xx) | x | xx (xx-xx) |
| Any Systemic Symptom | None | x | xx (xx-xx) | x | xx (xx-xx) | x | xx (xx-xx) | x | xx (xx-xx) | x | xx (xx-xx) | x | xx (xx-xx) | x | xx (xx-xx) |
| | Mild | x | xx (xx-xx) | x | xx (xx-xx) | x | xx (xx-xx) | x | xx (xx-xx) | x | xx (xx-xx) | x | xx (xx-xx) | x | xx (xx-xx) |
| | Moderate | x | xx (xx-xx) | x | xx (xx-xx) | x | xx (xx-xx) | x | xx (xx-xx) | x | xx (xx-xx) | x | xx (xx-xx) | x | xx (xx-xx) |
| | Severe | x | xx (xx-xx) | x | xx (xx-xx) | x | xx (xx-xx) | x | xx (xx-xx) | x | xx (xx-xx) | x | xx (xx-xx) | x | xx (xx-xx) |
| Fever | None | x | xx (xx-xx) | x | xx (xx-xx) | x | xx (xx-xx) | x | xx (xx-xx) | x | xx (xx-xx) | x | xx (xx-xx) | x | xx (xx-xx) |
| | Mild | x | xx (xx-xx) | x | xx (xx-xx) | x | xx (xx-xx) | x | xx (xx-xx) | x | xx (xx-xx) | x | xx (xx-xx) | x | xx (xx-xx) |
| | Moderate | x | xx (xx-xx) | x | xx (xx-xx) | x | xx (xx-xx) | x | xx (xx-xx) | x | xx (xx-xx) | x | xx (xx-xx) | x | xx (xx-xx) |
| | Severe | x | xx (xx-xx) | x | xx (xx-xx) | x | xx (xx-xx) | x | xx (xx-xx) | x | xx (xx-xx) | x | xx (xx-xx) | x | xx (xx-xx) |
| Feverishness | None | x | xx (xx-xx) | x | xx (xx-xx) | x | xx (xx-xx) | x | xx (xx-xx) | x | xx (xx-xx) | x | xx (xx-xx) | x | xx (xx-xx) |
| | Mild | x | xx (xx-xx) | x | xx (xx-xx) | x | xx (xx-xx) | x | xx (xx-xx) | x | xx (xx-xx) | x | xx (xx-xx) | x | xx (xx-xx) |
| | Moderate | x | xx (xx-xx) | x | xx (xx-xx) | x | xx (xx-xx) | x | xx (xx-xx) | x | xx (xx-xx) | x | xx (xx-xx) | x | xx (xx-xx) |
| | Severe | x | xx (xx-xx) | x | xx (xx-xx) | x | xx (xx-xx) | x | xx (xx-xx) | x | xx (xx-xx) | x | xx (xx-xx) | x | xx (xx-xx) |

| Symptom | Severity | Group 1 2013 3.75+AS03/ 2017 3.75+AS03 (D1-D22) (N=X) | | Group 2 2013 3.75+AS03/ 2017 3.75+AS03 (D1-D121) (N=X) | | Group 3 2013 3.75+AS03/ 2017 15 (D1-D121) (N=X) | | Group 4 2017 3.75+AS03/ 2017 3.75+AS03 (D1-D22) (N=X) | | Group 5 2017 3.75+AS03/ 2017 3.75+AS03 (D1-D121) (N=X) | | Group 6 2017 3.75+AS03/ 2017 15 (D1-D121) (N=X) | | All Subjects (N=X) | |
|------------|----------|--|---------------|---|---------------|--|---------------|--|---------------|---|---------------|--|---------------|-----------------------|---------------|
| | | n | % (95% CI) | n | % (95% CI) | n | % (95% CI) | n | % (95% CI) | n | % (95% CI) | n | % (95% CI) | n | % (95% CI) |
| Fatigue | None | x | xx (xx-xx) | x | xx (xx-xx) | x | xx (xx-xx) | x | xx (xx-xx) | x | xx (xx-xx) | x | xx (xx-xx) | x | xx (xx-xx) |
| | Mild | x | xx (xx-xx) | x | xx (xx-xx) | x | xx (xx-xx) | x | xx (xx-xx) | x | xx (xx-xx) | x | xx (xx-xx) | x | xx (xx-xx) |
| | Moderate | x | xx (xx-xx) | x | xx (xx-xx) | x | xx (xx-xx) | x | xx (xx-xx) | x | xx (xx-xx) | x | xx (xx-xx) | x | xx (xx-xx) |
| | Severe | x | xx (xx-xx) | x | xx (xx-xx) | x | xx (xx-xx) | x | xx (xx-xx) | x | xx (xx-xx) | x | xx (xx-xx) | x | xx (xx-xx) |
| Malaise | None | x | xx (xx-xx) | x | xx (xx-xx) | x | xx (xx-xx) | x | xx (xx-xx) | x | xx (xx-xx) | x | xx (xx-xx) | x | xx (xx-xx) |
| | Mild | x | xx (xx-xx) | x | xx (xx-xx) | x | xx (xx-xx) | x | xx (xx-xx) | x | xx (xx-xx) | x | xx (xx-xx) | x | xx (xx-xx) |
| | Moderate | x | xx (xx-xx) | x | xx (xx-xx) | x | xx (xx-xx) | x | xx (xx-xx) | x | xx (xx-xx) | x | xx (xx-xx) | x | xx (xx-xx) |
| | Severe | x | xx (xx-xx) | x | xx (xx-xx) | x | xx (xx-xx) | x | xx (xx-xx) | x | xx (xx-xx) | x | xx (xx-xx) | x | xx (xx-xx) |
| Myalgia | None | x | xx (xx-xx) | x | xx (xx-xx) | x | xx (xx-xx) | x | xx (xx-xx) | x | xx (xx-xx) | x | xx (xx-xx) | x | xx (xx-xx) |
| | Mild | x | xx (xx-xx) | x | xx (xx-xx) | x | xx (xx-xx) | x | xx (xx-xx) | x | xx (xx-xx) | x | xx (xx-xx) | x | xx (xx-xx) |
| | Moderate | x | xx (xx-xx) | x | xx (xx-xx) | x | xx (xx-xx) | x | xx (xx-xx) | x | xx (xx-xx) | x | xx (xx-xx) | x | xx (xx-xx) |
| | Severe | x | xx (xx-xx) | x | xx (xx-xx) | x | xx (xx-xx) | x | xx (xx-xx) | x | xx (xx-xx) | x | xx (xx-xx) | x | xx (xx-xx) |
| Arthralgia | None | x | xx (xx-xx) | x | xx (xx-xx) | x | xx (xx-xx) | x | xx (xx-xx) | x | xx (xx-xx) | x | xx (xx-xx) | x | xx (xx-xx) |
| | Mild | x | xx (xx-xx) | x | xx (xx-xx) | x | xx (xx-xx) | x | xx (xx-xx) | x | xx (xx-xx) | x | xx (xx-xx) | x | xx (xx-xx) |
| | Moderate | x | xx (xx-xx) | x | xx (xx-xx) | x | xx (xx-xx) | x | xx (xx-xx) | x | xx (xx-xx) | x | xx (xx-xx) | x | xx (xx-xx) |
| | Severe | x | xx (xx-xx) | x | xx (xx-xx) | x | xx (xx-xx) | x | xx (xx-xx) | x | xx (xx-xx) | x | xx (xx-xx) | x | xx (xx-xx) |
| Headache | None | x | xx (xx-xx) | x | xx (xx-xx) | x | xx (xx-xx) | x | xx (xx-xx) | x | xx (xx-xx) | x | xx (xx-xx) | x | xx (xx-xx) |
| | Mild | x | xx (xx-xx) | x | xx (xx-xx) | x | xx (xx-xx) | x | xx (xx-xx) | x | xx (xx-xx) | x | xx (xx-xx) | x | xx (xx-xx) |
| | Moderate | x | xx (xx-xx) | x | xx (xx-xx) | x | xx (xx-xx) | x | xx (xx-xx) | x | xx (xx-xx) | x | xx (xx-xx) | x | xx (xx-xx) |

| Symptom | Severity | Group 1 2013 3.75+AS03/ 2017 3.75+AS03 (D1-D22) (N=X) | | Group 2 2013 3.75+AS03/ 2017 3.75+AS03 (D1-D121) (N=X) | | Group 3 2013 3.75+AS03/ 2017 15 (D1-D121) (N=X) | | Group 4 2017 3.75+AS03/ 2017 3.75+AS03 (D1-D22) (N=X) | | Group 5 2017 3.75+AS03/ 2017 3.75+AS03 (D1-D121) (N=X) | | Group 6 2017 3.75+AS03/ 2017 15 (D1-D121) (N=X) | | All Subjects (N=X) | |
|-------------------|----------|--|---------------|---|---------------|--|---------------|--|---------------|---|---------------|--|---------------|-----------------------|---------------|
| | | n | % (95% CI) | n | % (95% CI) | n | % (95% CI) | n | % (95% CI) | n | % (95% CI) | n | % (95% CI) | n | % (95% CI) |
| | Severe | x | xx (xx-xx) | x | xx (xx-xx) | x | xx (xx-xx) | x | xx (xx-xx) | x | xx (xx-xx) | x | xx (xx-xx) | x | xx (xx-xx) |
| Nausea | None | x | xx (xx-xx) | x | xx (xx-xx) | x | xx (xx-xx) | x | xx (xx-xx) | x | xx (xx-xx) | x | xx (xx-xx) | x | xx (xx-xx) |
| | Mild | x | xx (xx-xx) | x | xx (xx-xx) | x | xx (xx-xx) | x | xx (xx-xx) | x | xx (xx-xx) | x | xx (xx-xx) | x | xx (xx-xx) |
| | Moderate | x | xx (xx-xx) | x | xx (xx-xx) | x | xx (xx-xx) | x | xx (xx-xx) | x | xx (xx-xx) | x | xx (xx-xx) | x | xx (xx-xx) |
| | Severe | x | xx (xx-xx) | x | xx (xx-xx) | x | xx (xx-xx) | x | xx (xx-xx) | x | xx (xx-xx) | x | xx (xx-xx) | x | xx (xx-xx) |
| Any Local Symptom | None | x | xx (xx-xx) | x | xx (xx-xx) | x | xx (xx-xx) | x | xx (xx-xx) | x | xx (xx-xx) | x | xx (xx-xx) | x | xx (xx-xx) |
| | Mild | x | xx (xx-xx) | x | xx (xx-xx) | x | xx (xx-xx) | x | xx (xx-xx) | x | xx (xx-xx) | x | xx (xx-xx) | x | xx (xx-xx) |
| | Moderate | x | xx (xx-xx) | x | xx (xx-xx) | x | xx (xx-xx) | x | xx (xx-xx) | x | xx (xx-xx) | x | xx (xx-xx) | x | xx (xx-xx) |
| | Severe | x | xx (xx-xx) | x | xx (xx-xx) | x | xx (xx-xx) | x | xx (xx-xx) | x | xx (xx-xx) | x | xx (xx-xx) | x | xx (xx-xx) |
| Pain | None | x | xx (xx-xx) | x | xx (xx-xx) | x | xx (xx-xx) | x | xx (xx-xx) | x | xx (xx-xx) | x | xx (xx-xx) | x | xx (xx-xx) |
| | Mild | x | xx (xx-xx) | x | xx (xx-xx) | x | xx (xx-xx) | x | xx (xx-xx) | x | xx (xx-xx) | x | xx (xx-xx) | x | xx (xx-xx) |
| | Moderate | x | xx (xx-xx) | x | xx (xx-xx) | x | xx (xx-xx) | x | xx (xx-xx) | x | xx (xx-xx) | x | xx (xx-xx) | x | xx (xx-xx) |
| | Severe | x | xx (xx-xx) | x | xx (xx-xx) | x | xx (xx-xx) | x | xx (xx-xx) | x | xx (xx-xx) | x | xx (xx-xx) | x | xx (xx-xx) |
| Tenderness | None | x | xx (xx-xx) | x | xx (xx-xx) | x | xx (xx-xx) | x | xx (xx-xx) | x | xx (xx-xx) | x | xx (xx-xx) | x | xx (xx-xx) |
| | Mild | x | xx (xx-xx) | x | xx (xx-xx) | x | xx (xx-xx) | x | xx (xx-xx) | x | xx (xx-xx) | x | xx (xx-xx) | x | xx (xx-xx) |
| | Moderate | x | xx (xx-xx) | x | xx (xx-xx) | x | xx (xx-xx) | x | xx (xx-xx) | x | xx (xx-xx) | x | xx (xx-xx) | x | xx (xx-xx) |
| | Severe | x | xx (xx-xx) | x | xx (xx-xx) | x | xx (xx-xx) | x | xx (xx-xx) | x | xx (xx-xx) | x | xx (xx-xx) | x | xx (xx-xx) |
| Pruritus | None | x | xx (xx-xx) | x | xx (xx-xx) | x | xx (xx-xx) | x | xx (xx-xx) | x | xx (xx-xx) | x | xx (xx-xx) | x | xx (xx-xx) |

